NCT06831786

Study Protocol

Official Title:

Co-administration of COVID-19 and Influenza Vaccines: A Pilot Randomized Controlled Trial in Healthy Adults

NCT Number: NCT06831786

Document Type: Study Protocol

Document Date: 2 January 2024

Sponsor/Institution: Faculty of Medicine, Prince of Songkla University, Hat Yai, Thailand

Background

Coronavirus disease 2019 (COVID-19) was declared a pandemic by the World Health Organization (WHO) in March 2020, owing to its rapid global spread and the resulting high rates of illness and death. In May 2023, the WHO indicated that the COVID-19 public health emergency of international concern had concluded, officially marking the end of the pandemic [1]. However, COVID-19 remains a persistent disease and is now transitioning toward an endemic status [1]. Control of COVID-19 transmission was achieved through herd immunity from vaccination or previous infection. The Centers for Disease Control and Prevention advises annual updates for both COVID-19 and flu vaccinations [2]. Recent studies suggest that the influenza vaccine may help reduce COVID-19 infection rates and related deaths [3–6]. Analyses at the national level in the United States have shown an inverse relationship between flu vaccine coverage in older adults and COVID-19 deaths [7]; similar results were observed in Italy [8]. The protective effect could be explained by cross-reactive immunity, which is mediated by memory T-cells triggering both cell-mediated immune response (CMIR) and humoral immune response (HIR) [9]. A previous study identified cross-reactive antibodies between glycan epitopes of the COVID-19 virus spike protein and the influenza virus surface protein. Although non-neutralizing antibodies, they may facilitate antibody-dependent cellular cytotoxicity [10]. Another proposed mechanism involves the broad immunological effects of vaccines, which enhance trained immunity by modifying the gene expression patterns of innate immune cells [11]. A previous study reported markedly higher immunity against severe acute respiratory syndrome coronavirus 2 (SARS-CoV-2) neutralization titers among workers vaccinated with both flu and pneumococcal vaccines or with the flu vaccine alone [12]. Another study found higher levels of anti-spike receptor-binding domain (RBD) antibodies in individuals who received the flu vaccine, in contrast to those who were unvaccinated before receiving the BNT162b2 vaccine [13].

Additionally, six randomized controlled trials (RCTs) examined the safety or immunogenicity of administering mRNA COVID-19 doses alongside influenza vaccines [14–19]. All these studies have confirmed the safety of administering the vaccines together; however, the findings on immunogenicity were mixed. Out of the six RCTs, five evaluated HIR and observed reduced anti-SARS-CoV-2 antibody concentrations in those receiving both vaccines [15–19]. Only two studies met the non-inferiority margin for immunogenicity outcomes [15, 18]. However, none have yet evaluated CMIR.

Owing to the lack of prior research evaluating CMIR, we conducted a pilot study to assess both HIR and CMIR for COVID-19 and influenza vaccines administered together compared with individually administering each vaccine. We hypothesized that the CMIR may be stronger in the co-administration group, which could help explain the reduced mortality from COVID-19 infections reported in previous studies for patients vaccinated with the influenza vaccine. If confirmed, a stronger CMIR may serve as a proof-of-concept, demonstrating the potential immunological benefits of vaccine co-administration. Additionally, our study may provide insightful findings on the co-administration policy, the implementation of which may increase vaccine coverage and reduce healthcare burden.

Objectives

Primary Objective:

- To evaluate and compare post-vaccination cell-mediated immune responses (CMIR) and humoral immune responses (HIR) between participants receiving co-administration of COVID-19 and influenza vaccines versus COVID-19 vaccine alone.

Secondary Objectives:

- To assess the magnitude of immune responses within each study group.
- To compare the magnitude of immune enhancement between groups.
- To evaluate the frequency and severity of adverse events following vaccination.

Study Design and Participants

This was a pilot, single-blind, randomized controlled trial conducted at Songklanagarind Hospital, Faculty of Medicine, Prince of Songkla University, Hat Yai, Thailand. Eligible participants were healthy adult volunteers aged 18–60 years.

Inclusion Criteria

- Thai adults aged 18–60 years who had received COVID-19 and influenza vaccines more than 6 months prior.
- Able and willing to comply with trial requirements, including 1-month follow-up.
- In good health at enrollment as judged by medical history, physical exam, and investigator assessment.
- Able to provide informed consent and sign the ICF.

Exclusion Criteria

- History of influenza or COVID-19 infection within 6 months.
- History or family history of convulsions, epilepsy, encephalopathy, or psychosis.
- Allergy to vaccine components or prior severe hypersensitivity reactions.
- History of Guillain-Barré syndrome.
- Positive pregnancy test, pregnant, breastfeeding, or pregnancy plan within 6 months.
- Infectious diseases including HIV or suspected SARS-CoV-2 infection.
- Prior SARS-CoV-2 infection within 6 months.
- Severe uncontrolled chronic diseases (e.g., poorly controlled diabetes mellitus, uncontrolled hypertension).
- History of urticaria within 1 year before vaccination.
- Known coagulation disorders or thrombocytopenia contraindicating intramuscular injection.
- Needle phobia.
- Use of immunosuppressive therapy, cytotoxic therapy, or systemic corticosteroids.
- Receipt of blood products within 4 months before vaccination.

- Ongoing anti-tuberculosis treatment.
- Inability to follow protocol or understand informed consent, as judged by investigator.

Interventions

Arm 1 – Active Comparator: Bivalent mRNA COVID-19 vaccine (BNT162b2)

- Intervention: Biological/Vaccine – Bivalent mRNA SARS-CoV-2 vaccine
- Description: Administering a booster dose of the bivalent mRNA vaccine BNT162b2 (Pfizer, Bangkok, Thailand).

Arm 2 – Experimental: Quadrivalent Influenza Vaccine

- Intervention: Biological/Vaccine – Quadrivalent influenza vaccine
- Description: Administering a VaxigripTetra™ (Sanofi-Aventis, Bangkok, Thailand).

Arm 3 – Experimental: Co-administration

- Interventions:
 - Biological/Vaccine – Bivalent mRNA SARS-CoV-2 vaccine (BNT162b2)
 - Biological/Vaccine – Quadrivalent influenza vaccine (VaxigripTetra™)
- Description: Co-administering both vaccines intramuscularly, either in different arms or in the same arm at least 25.4 mm apart.

Outcomes

Primary Outcomes

- **Cell-mediated immune response (CMIR):** Post-vaccination interferon-gamma enzyme-linked immunospot (IFN- γ ELISpot) assay results comparing the co-administration group with the COVID-19 vaccine-only group.
- **Humoral immune response (HIR):** Post-vaccination anti-receptor-binding domain immunoglobulin G (anti-RBD IgG) concentrations comparing the co-administration group with the COVID-19 vaccine-only group.
- **Non-inferiority margin:** Defined as the lower bound of the 95% confidence interval for the geometric mean ratio (GMR) >0.67 , consistent with WHO vaccine evaluation guidelines.

Secondary Outcomes

- **Magnitude of immune response within each group:** GMR comparing pre- and post-vaccination values (GMRpost/pre) for both CMIR and HIR.
- **Comparison of immune enhancement between groups:** Ratio of GMRpost/pre values across groups.
- **Adverse events (AEs):** Incidence, type, and severity of local and systemic solicited AEs at 1 and 4 weeks, as well as unsolicited and serious AEs.

Study Procedures

Eligible volunteers provided written informed consent before participation. Participants were randomized in a 1:1:1 ratio, using block randomization (block size of 6) generated with R Statistical Software, to receive:

1. Bivalent mRNA COVID-19 vaccine (BNT162b2, Pfizer) alone,
2. Quadrivalent influenza vaccine (VaxigripTetra™, Sanofi-Aventis) alone, or
3. Both vaccines administered concurrently.

Vaccines were administered intramuscularly, either in different arms or in the same arm with injection sites at least 25.4 mm apart.

Blood samples were collected at baseline (Day 0, prior to vaccination) and at Day 28. Samples were used for measurement of:

- Humoral immune response (HIR): anti-receptor binding domain (RBD) IgG levels.
- Cell-mediated immune response (CMIR): IFN- γ enzyme-linked immunospot (ELISpot) assay.

Participants were monitored for immediate adverse reactions for 30 minutes after vaccination. Active follow-up was conducted at 1- and 4-weeks post-vaccination to assess solicited local and systemic adverse events, and unsolicited or serious adverse events were documented throughout the study period.

Sample Size

A total of 36 participants was planned. The sample size followed Julious' rule-of-thumb[20] for pilot studies (≥ 12 per group) to obtain stable variance estimates and inform the design of a subsequent adequately powered non-inferiority RCT. The study was not powered for confirmatory hypothesis testing; non-inferiority analyses are exploratory. Estimates from this pilot (means, variances, GMRs) will guide the definitive trial's sample-size calculation.

Statistical Methods

Analysis Population

- All randomized participants who received at least one dose of study vaccine were included in the immunogenicity and safety analyses (modified intention-to-treat).

Data Handling and Transformation

- Immune response outcomes (IFN- γ ELISpot and anti-RBD IgG antibody levels) were log-transformed prior to analysis to normalize distributions and stabilize variance.
- Zero values were replaced with 1 to allow logarithmic transformation.

Primary Analysis

- Geometric mean ratios (GMRs) of post-vaccination responses were calculated to compare the co-administration group with the COVID-19 vaccine-only group.
- Non-inferiority was concluded if the lower bound of the two-sided 95% confidence interval (CI) exceeded **0.67**, consistent with WHO vaccine evaluation guidelines.

Secondary Analyses

1. **Magnitude of immune response (within-group):**
 - Calculated as GMRpost/pre for both CMIR and HIR.
 - Paired t-tests were used to assess the significance of pre- vs post-vaccination changes.
2. **Between-group comparisons (ratio of magnitude):**
 - Ratios of GMRpost/pre between study groups were calculated to compare immune enhancement.
3. **Safety analysis:**
 - Incidences of solicited local and systemic adverse events were summarized by frequency and percentage.
 - Group comparisons used Chi-square or Fisher's exact tests, as appropriate.

Software

- All statistical analyses were conducted using **R Statistical Software, version 4.3.2** (R Foundation for Statistical Computing, Vienna, Austria).

Laboratory Methods

- **Antibody analysis:** Anti-SARS-CoV-2 RBD IgG (Wuhan-Hu-1 strain) will be measured by chemiluminescent microparticle immunoassay (Abbott, Abbott Park, IL, USA). Results in arbitrary units (AU/mL) will be converted to WHO binding antibody units (BAU/mL) using $1 \text{ BAU/mL} = 0.142 \text{ AU/mL}$.
- **Ex vivo IFN- γ ELISpot assays:** Peripheral blood mononuclear cells (PBMCs) will be stimulated with SARS-CoV-2 spike peptide pools (Wuhan strain) and assessed in triplicate wells. Spot-forming cells (SFCs) per 10^6 PBMCs will be quantified using an automated ELISpot counter (AID Diagnostika, Konstanz, Germany), subtracting background from negative controls.

Adverse Event Monitoring

All participants were observed on-site for 30 minutes post-vaccination to detect any immediate reactions.

Solicited Adverse Events (AEs):

- Local AEs: pain, redness, swelling, and palpable mass at the injection site.
- Systemic AEs: fever, myalgia, malaise, headache, nausea, and other constitutional symptoms.

- These pre-specified solicited AEs were actively assessed at 1 week and 4 weeks after vaccination.

Unsolicited and Serious Adverse Events (SAEs):

- Any unsolicited AE reported during the study period was documented.
- SAEs were recorded throughout the follow-up period, with severity grading and assessment of relationship to study vaccines.

Ethics and Dissemination

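### Does the undefined single-blind label, with two injections in one arm and one in the others, call for a change to the plan?

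*Combined protocol and SAP*

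**What the plan says.** Study Design and Participants contains the only statement on masking in this trial: "This was a pilot, single-blind, randomized controlled trial". No section says who is blinded or by what means. Otherwise, blinding and placebo appear only in the titles of cited studies.

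Under Interventions, Arm 1 is described as "Administering a booster dose of the bivalent mRNA vaccine BNT162b2" and Arm 2 as the quadrivalent influenza vaccine. Arm 3 is described as "Co-administering both vaccines intramuscularly, either in different arms or in the same arm at least 25.4 mm apart". Study Procedures says that each single vaccine is given on its own, and repeats the site rule: "Vaccines were administered intramuscularly, either in different arms or in the same arm with injection sites at least 25.4 mm apart". Neither section lists a placebo or sham injection.

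Adverse events are a secondary outcome, solicited at 1 and 4 weeks. The solicited lists under Adverse Event Monitoring are "Local AEs: pain, redness, swelling, and palpable mass at the injection site" and "Systemic AEs: fever, myalgia, malaise, headache, nausea, and other constitutional symptoms". The safety analysis in Statistical Methods says "Group comparisons used Chi-square or Fisher's exact tests, as appropriate", with no significance level and no rule that turns a result into a decision.

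The two primary outcomes are measured in the laboratory. Anti-RBD IgG is read by a chemiluminescent immunoassay, and ELISpot spots "will be quantified using an automated ELISpot counter".

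**The concern.** Single-blind usually means that the participant does not know the allocation. A participant who gets two injections knows that it was not one. Taken in that sense, the label cannot hold between Arm 3 and either single-vaccine arm as the interventions are described. It could hold only between Arms 1 and 2.

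What is at stake is the reading of the safety results. Pain, myalgia, malaise, headache and nausea depend on what the participant says. Someone who knows that two vaccines were given may expect, notice or report more symptoms. A reader who takes the label at face value would assume a protection that the comparison of co-administration with COVID-19 vaccine alone may not have. The Background says that the study may inform co-administration policy, so tolerability will be read with interest.

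**Working it through.** **1. The plan's own figure.** Sample Size gives 36 participants and at least 12 per group; randomization is 1:1:1. 3 × 12 = 36, which reproduces the stated total. The number comes from a pilot rule of thumb and uses no assumption about masking, so naming the masked party would not move it.

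**2. Injections by arm (Interventions, Study Procedures).** Arm 1: one. Arm 2: one. Arm 3: two, at separate sites. The count separates Arm 3 from the others for the participant, unless a sham was used that the document does not describe. The wording for the single-vaccine arms makes a sham unlikely but does not exclude it.

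**3. Possible meanings of the label.**

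| Masked party | Compatible with the described design? | Outcome protected |
|---|---|---|
| Participant | Only Arm 1 vs Arm 2, absent a sham | Self-reported events in that contrast |
| Adverse event assessor | Possible; the mode of assessment (visit, telephone, diary) is not given | Grading and recording of events |
| Laboratory staff | Yes | Both co-primary outcomes |

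Two of the three readings fit the design. The text does not choose between them.

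**4. Where knowledge of allocation could act.** The lists name 4 local and 5 systemic events, 4 + 5 = 9. By my classification 5 of the 9 are purely subjective (pain, myalgia, malaise, headache, nausea). This is a rough guide only: the systemic list is open-ended, and if redness, swelling or fever were collected by recall, they too would rest on the participant's report.

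**5. Scale at 12 per arm.** One changed report moves an arm's proportion by 1/12 = 8.3 percentage points. The plan sets no significance level for adverse events; I assume two-sided 0.05. For Fisher's exact test at 12 vs 12, examples of the smallest Arm 3 count that reaches p < 0.05, for a given Arm 1 count, are:

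| Arm 1 events | Arm 3 events | p | Excess |
|---|---|---|---|
| 0 | 5 | 0.037 | 5 |
| 1 | 7 | 0.027 | 6 |
| 3 | 9 | 0.039 | 6 |
| 6 | 12 | 0.014 | 6 |
| 7 | 12 | 0.037 | 5 |

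With 8 or more events in Arm 1, no Arm 3 excess reaches it.

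**6. Chance of a significant result from reporting bias alone.** The documents give no event rates, so I assume a true rate p of 20% to 50% in both arms and let knowledge of allocation add d to the Arm 3 reporting rate. The probability is the sum, over all pairs (a, b) with Fisher p < 0.05, of Bin(a; 12, p) × Bin(b; 12, p + d).

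| Added reporting d | Expected extra reports, 12 × d | Probability of p < 0.05 |
|---|---|---|
| 0 | 0 | 1.2% to 2.3% |
| 10 points | 1.2 | 3.2% to 3.9% |
| 20 points | 2.4 | 9.2% to 9.7% |
| 30 points | 3.6 | 21.0% to 21.1% |

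A modest bias would show mainly in the descriptive percentages. A large one would produce some spurious significant results. The documents do not say which applies, or even in which direction a bias would run.

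**7. What naming the masked party would alter.** The total of 36, the geometric mean ratio comparison, the 0.67 margin, the within-group paired tests and the safety tests all stay as they are. No stopping or decision rule depends on adverse event counts.

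**The case for a change.** The best case for a change is this. Adverse event frequency and severity is a stated secondary objective, and between-group tests are planned for it. Co-administration against COVID-19 vaccine alone is the trial's main contrast for immunogenicity, and a reader will look at tolerability in the same contrast. An unqualified label suggests protection that participants in that contrast probably did not have. The pilot is meant to inform a definitive trial, so a vague masking scheme could be carried forward. The remedy would be one sentence, plus coded samples if assays are still to be run.

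Part of this stands. The label is undefined. Unless an undescribed sham was used, participant-reported comparisons involving Arm 3 should be read as unmasked at participant level.

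The rest is weaker. It does not follow that assessor masking would fail for local reactions: the plan lists events at the injection site but does not say that an assessor examined it. Coded samples would answer a risk that the plan does not show, since nothing says that laboratory staff know the allocation, and the label may already mean that they do not. Much of the document is in the past tense, so coding may also come too late. A clearer sentence would improve the description but would remove no bias from the reports.

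**Conclusion.** The observation is accurate, but no change to the plan follows. The masked party is missing from the text. Supplying it would be a reporting clarification with no effect on conduct, analysis or decision. The co-primary outcomes are laboratory assays, little exposed to what participants know. The outcome that is exposed is secondary, has no decision rule, and sits in a pilot of 12 per arm whose non-inferiority analyses are themselves labelled exploratory. Doing without a sham injection is a fair trade-off in a study of this size. Analysts who know how the trial was run can state who was masked when they report it, and can read symptom comparisons with the co-administration arm accordingly.

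The size of any bias is unknown. Under the assumptions shown (true rate 20% to 50%, two-sided 0.05), 10 to 30 points of inflated reporting add 1.2 to 3.6 reports among 12 participants and give a significant Fisher result in about 3% to 21% of trials, against 1% to 2% without bias. False significance is therefore not excluded; it depends on a bias that cannot be estimated here. The conclusion rests on no sham having been used, on adverse event results not driving any decision, and on the assays being read as Laboratory Methods describes.

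### Should the plan say now how the pilot's log SD and observed GMR will be used to size the definitive trial?

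*Combined protocol and SAP*

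**What the plan says.** The Sample Size section fixes the number and its reason: "A total of 36 participants was planned", and "The sample size followed Julious' rule-of-thumb[20] for pilot studies", with at least 12 in each of three groups. The aim is "to obtain stable variance estimates and inform the design of a subsequent adequately powered non-inferiority RCT". The same section states that the study has no power for confirmatory testing and that its non-inferiority analyses are exploratory. It ends: "Estimates from this pilot (means, variances, GMRs) will guide the definitive" trial's sample size.

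Under Statistical Methods, Primary Analysis compares post-vaccination geometric means between co-administration and COVID-19 vaccine alone: "Non-inferiority was concluded if the lower bound of the two-sided 95% confidence interval (CI) exceeded" 0.67. An interval for the between-group GMR is therefore planned. No section plans an interval for the log-scale SD, and none says which GMR the later trial should assume.

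The Background points in different directions for the two primary outcomes. Of six earlier co-administration trials, "five evaluated HIR and observed reduced anti-SARS-CoV-2 antibody concentrations in those receiving both vaccines". For cell-mediated immunity, which none of the six evaluated, the expectation is the reverse: "We hypothesized that the CMIR may be stronger in the co-administration group".

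**The concern.** Informing the next trial is the reason given for the sample size, so how the estimates carry forward looks like part of the plan. Twelve per arm gives an SD good only to within a factor of about 1.4 upwards, and required n goes with its square. Listing GMRs among the estimates that will guide the calculation also leaves open that the observed ratio becomes the planning effect. At this size the ratio is very noisy. A lucky pilot GMR would give a definitive trial that is too small, and an unlucky one would suggest that no trial is feasible. A single planning GMR might also suit neither outcome, since antibody is expected to fall and the cellular response to rise. At stake would be the power of the definitive trial.

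**Working it through.** **The plan's own figure.** 3 groups × 12 = 36, which reproduces. There is no power-based figure to check.

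**Inputs from the protocol.** 12 per arm in the two primary arms, so df = 24 − 2 = 22 if every Day 28 sample is available; margin 0.67, so −ln 0.67 = 0.4005; two-sided 95% interval, so z = 1.960.

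**Assumptions not in the protocol.** Margin carried over to the definitive trial; target power 90% (z = 1.2816, sum 3.2415); natural-log SD 0.5 to 1.5; true GMR 0.9 or 1.0; no dropout.

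**1. Precision of the SD.** Limits are s·√(df/χ²).

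| Limit | χ² quantile (22 df) | SD multiplier | n multiplier |
|---|---|---|---|
| Lower 95% | 36.78 | 0.773 | 0.598 |
| Upper 95% | 10.98 | 1.415 | 2.003 |
| One-sided 80% upper | 16.31 | 1.161 | 1.349 |

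Illustration with observed SD 1.0 and planning GMR 1.0: n per arm = 2 × 1.0² × 3.2415² / 0.4005² = 131.0, so 132. The 95% limits give 79 and 263; the 80% upper limit gives 177.

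**2. Consequence of using the SD point estimate, with the GMR right.** True power falls below 80% when χ²₂₂ < 22 × [(1.960 + 0.842)/(3.2415·m)]², where m is the multiplier applied to s.

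- m = 1: threshold 16.43, probability 20.6%; mean power 87%.
- m = 1.161: threshold 12.19, probability 4.7%; mean power 94%.

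These shares depend on the target. Sized for 80% power instead, true power is below 80% in 54% of pilots with m = 1 and 20% with m = 1.161; it is below 70% in 25% and 6%.

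**3. Consequence of using the observed GMR directly.** This is hypothetical, since the plan does not say it will be done. SE of the log GMR = SD·√(2/12). No n exists if the observed GMR is 0.67 or lower. Otherwise n = 2s² × 3.2415² / (ln observed GMR − ln 0.67)². From 2,000,000 simulated pilots per row:

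| True GMR | Log SD | No n exists | Power below 80%, of the rest |
|---|---|---|---|
| 1.0 | 0.5 | 2.5% | 40% |
| 1.0 | 1.0 | 16% | 53% |
| 0.9 | 0.5 | 7% | 45% |
| 0.9 | 1.0 | 23% | 60% |

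**4. Is any information lost?** Assuming a pooled t interval, the planned GMR interval has log half-width 2.074 × s × √(2/12) = 0.847·s. At s = 1.0 and an observed GMR of 1.0 it reads 0.43 to 2.33. A reader divides the log half-width by 0.847 to recover s, then applies the multipliers in step 1. The variances are named as pilot estimates in any case.

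**5. Would a rule fixed now do better?** Take a true GMR of 0.9 and size on the 80% upper limit. The chance of power below 80% is 56.6% if the planning GMR is 1.0, 24.0% at 0.95 and 4.7% at 0.90. The cost, relative to n at GMR 1.0 on the point-estimate SD:

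- GMR 0.95: [0.4005/ln(0.95/0.67)]² = 1.315; × 1.349 = 1.77 times.
- GMR 0.90: [0.4005/ln(0.90/0.67)]² = 1.841; × 1.349 = 2.48 times.

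A fixed planning value is protective only if it is chosen well, and protection is paid for in participants.

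**The case for a change.** The best case for a change is that a rule written before the estimates are known cannot be picked afterwards to suit them. It would take a few sentences and need no new data. Step 2 needs no unusual reading of the plan, only that the point-estimate SD is used. The Background itself gives grounds for treating the two outcomes separately and for showing GMRs below 1.

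The silence is real and the SD arithmetic stands. The rest is weaker:

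- *Guide* states no wrong rule. It is compatible with an upper limit, a range of GMRs, or use of the pilot GMR for sensitivity only. GMR in this protocol also covers the post/pre ratios, so the word need not mean the planning effect.
- The cases in which no n exists announce themselves and cannot produce an undersized trial.
- Barring the observed GMR is debatable for the cellular outcome. The Background says none of the six earlier trials evaluated it, so the pilot may be the only direct evidence on co-administration.
- An 80% limit is one choice among several. For ELISpot, replacing zeros with 1 makes it approximate: with an assumed 5% of values so replaced (log SD 1.0, log mean ln 50 or ln 100), it covered the true SD in 72% and 69% of simulated pilots.

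**Conclusion.** No change to the plan is needed. It leaves unwritten a policy for a trial not yet designed; it does not prescribe a faulty one. N = 36, the primary comparison and its interval are as they would be under any such policy, and nothing has to be collected or analysed differently now for the later team to allow for SD uncertainty.

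The imprecision is real: 0.77 to 1.42 times the SD, and 0.60 to 2.00 times n. Those multipliers rest only on 22 degrees of freedom and roughly normal log values. The power shares rest further on the assumed target power and the carried-over margin, and those for direct use of the observed GMR also on the assumed log SD, true GMR and a practice the plan does not state.

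How much to inflate the SD, and which GMR to plan on for each outcome, are trade-offs between size and risk. They belong in the definitive trial's protocol, where the margin and target power will be set. Reporting each log SD with its 95% interval from the two primary arms would be useful in the pilot's report, but analysts can do so without an amendment.

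### Does the pilot need a second, evaluable immunogenicity set beside the dosed (modified intention-to-treat) set?

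*Combined protocol and SAP*

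**What the plan says.** Under Statistical Methods, Analysis Population, a single bullet defines the set: "All randomized participants who received at least one dose of study vaccine were included in the immunogenicity and safety analyses". It is labelled modified intention-to-treat. The Primary Analysis section names no other set for the GMR of co-administration against COVID-19 vaccine alone, and gives the decision rule: "Non-inferiority was concluded if the lower bound of the two-sided 95% confidence interval (CI) exceeded" 0.67.

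The Sample Size section limits what the result is for: "The study was not powered for confirmatory hypothesis testing; non-inferiority analyses are exploratory". It then says "Estimates from this pilot (means, variances, GMRs) will guide the definitive" trial's sample size.

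On dosing, the third arm in Study Procedures is "Both vaccines administered concurrently". On infection, the Exclusion Criteria list "Prior SARS-CoV-2 infection within 6 months", and no rule applies after Day 0. Follow-up is not empty, however: "Active follow-up was conducted at 1- and 4-weeks post-vaccination to assess solicited local and systemic adverse events", with unsolicited and serious events documented throughout. Under Laboratory Methods, the antibody assay is anti-RBD IgG, and for ELISpot the cells "will be stimulated with SARS-CoV-2 spike peptide pools (Wuhan strain) and assessed in triplicate wells". Both readouts are directed at spike.

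**The concern.** There are three reasons to worry.

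- The one-dose threshold means fully dosed in the two single-vaccine arms, but not in the co-administration arm. Someone there who received only the COVID-19 vaccine would pull the GMR toward 1, which favours non-inferiority. Someone who received only the influenza vaccine would probably pull it down.
- Recent infection is screened out at entry and then disregarded until Day 28. Because both assays target spike, they cannot tell an infection from a vaccine response.
- The pilot's product is its means, variances and GMRs. With 12 values per arm, one aberrant value carries weight, and a distorted variance would pass into the size of the definitive trial.

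Vaccine immunogenicity trials often report an evaluable set beside the dosed set for these reasons, so its absence is noticeable.

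**Working it through.** **Inputs from the documents.** 36 participants, 1:1:1, so 36 / 3 = 12 per arm, which matches the stated rule of at least 12 per group. Margin 0.67, two-sided 95% CI. The plan states no SD, infection rate or deviation rate.

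**Assumptions.** Natural-log SD 0.5, 0.8 or 1.0; one affected participant; an infection multiplies the Day 28 value by f = 3, 5 or 10. For the definitive trial: true GMR 1, margin 0.67, 80% power, noncentral t.

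**Step 1: partial dosing.** Take a true GMR of 0.67, where a non-inferiority conclusion is false and the nominal rate is 2.5%.
- One COVID-only participant in the co-administration arm: expected GMR 0.67^(11/12) = 0.69. Simulation (400,000 trials per setting) gives false non-inferiority of 3.4%, 3.1% and 3.0% at SD 0.5, 0.8 and 1.0.
- One influenza-only participant, response assumed 5-fold lower: 0.67 × 5^(−1/12) = 0.59, with rates of 0.2%, 0.6% and 0.9%.

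Both require one of two injections planned for the same occasion to be missed.

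**Step 2: infection and the GMR.** One value shifted by f multiplies that arm's geometric mean by f^(1/12) = 1.10, 1.14 or 1.21. The GMR is multiplied by this if the case is in the co-administration arm and divided by it if in the control arm. Averaged over the two arms, false non-inferiority is 2.0% to 2.5%, so there is no systematic inflation.

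**Step 3: infection and the variance.** The affected arm's expected sample variance rises by (ln f)²/12, and the pooled variance by half of that. The ratio is 1 + (ln f)² / (24 × SD²). For f = 10 and SD 0.8: 1 + 5.302 / (24 × 0.64) = 1.345.

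**Step 4: sampling noise with no deviation at all.** With 22 degrees of freedom, the pooled variance estimate lies between 10.98/22 = 0.50 and 36.78/22 = 1.67 times the truth in 95% of trials. The CI factor around the GMR is exp(2.074 × SD × √(2/12)).

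| ln-SD | Variance ratio, f = 3 / 5 / 10 | Definitive n per arm: none, then f = 3 / 5 / 10 | 95% range of n from sampling alone | 95% CI factor for GMR |
|---|---|---|---|---|
| 0.5 | 1.20 / 1.43 / 1.88 | 26, then 31 / 37 / 48 | 14 to 42 | 1.53 |
| 0.8 | 1.08 / 1.17 / 1.345 | 64, then 69 / 75 / 86 | 33 to 106 | 1.97 |
| 1.0 | 1.05 / 1.11 / 1.22 | 99, then 104 / 110 / 121 | 50 to 165 | 2.33 |

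In eight of the nine cells, the n shifted by one infection stays inside the range that sampling alone produces. The exception is SD 0.5 with a 10-fold boost (48 against an upper limit of 42). The GMR factor, at most 1.21, is below the CI factor in every row.

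**Step 5: how often the sets would differ through infection.** At an assumed Day 0 to Day 28 infection risk of 1%, 2% or 5%, the chance of at least one infection among the 24 compared is 1 − (1 − p)^24 = 21%, 38% or 71%. These count all infections. The plan lists no post-baseline infection test and no non-spike marker, so only documented cases could be removed, and the sets would differ less often than this.

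**Step 6: what a second set costs.** At SD 0.8 the CI factor widens from 1.97 with 12 per arm to 2.04 with 11 and 2.12 with 10. The set also conditions on events after randomization.

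**The case for a change.** The strongest case for a change is that it is nearly free. The dosed set would stay primary, one analysis would be repeated, and records from the existing week 1 and week 4 contacts would supply the exclusions. Unlike sampling error, a documented infection can be identified, and its expected effect on the variance is upward whichever arm it falls in. The plan already treats recent infection as a confounder at entry, so following that through to Day 28 is consistent.

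Part of this stands. No pre-specified analysis uses information on dosing or infection after Day 0, and reporting such cases by arm would be good practice. Three points limit it.

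- The events are not invisible. Solicited systemic symptoms are actively assessed at weeks 1 and 4, other events are recorded, and a 10-fold outlier among 12 values can be inspected. An analyst who finds a documented infection or a missed injection can report it and rerun the GMR without that participant; the plan does not prevent this.
- Upward variance inflation makes a definitive trial larger, not underpowered.
- It is not clear that the SD from an evaluable set is the better planning input. If the definitive trial is also analysed by modified intention-to-treat, its participants can be infected too, and an SD stripped of such cases could leave it too small. Statisticians would differ on this.

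**Conclusion.** No change follows. The gap is real, but the analysis as written is sound for a pilot whose non-inferiority comparison is declared exploratory. Partial dosing is unlikely when both vaccines are given concurrently; one COVID-only participant raises false non-inferiority to 3.4% at most, against 2.5%. Infection has no fixed direction for the GMR. At an assumed log-SD of 0.8 its effect on the planned definitive size (64 to between 69 and 86 per arm) is well within the 33 to 106 that chance alone produces. Only a low SD of 0.5 combined with a 10-fold boost goes beyond the pilot's noise.

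A second set would have no decision role, would miss undocumented infections, and would equal the dosed set whenever no deviation was recorded. Describing deviations and documented infections by arm, with a sensitivity analysis if any occur, is ordinary reporting that analysts can do without amending the plan. The conclusion rests on the assumed SDs, fold boosts and single affected participant; several documented infections in one arm would deserve explicit comment in the report.
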